8.5 Study size

The sample size is not based on any formal calculation. All patients enrolled in the Pharmachild JIA registry study before September 30, 2018 meeting the criteria defined for the study population will be included in the study.

It is estimated that approximately 300 patients may be included.

8.6 Data management

In the Pharmachild registry data have been collected on-line via the secured PRINTO website. The web system is accessible only to authorized personnel through unique individual usernames and passwords.

Data are cleaned and remotely monitored by designated PRINTO personnel on an ongoing basis to check the accuracy of data. If necessary, additional and more precise information can be requested by the PRINTO personnel.

Technical management of the database is handled by PRINTO.

No individual patient listings will be obtained for this study, only summary output will be reported.

Statistical analyses will be performed using SAS software Version 9.3 or later (SAS Institute Inc, Cary, North Carolina, United States).

8.7 Data analysis

Patient characteristics at start of Kineret treatment will be summarized and presented.

There will be five main analysis sets:

- The complete set, including all patients with SJIA in the registry who have received Kineret at least once following a diagnosis of SJIA as per investigator judgement and enrolled before the cut-off date for the current study (September 30, 2018).
- The long-term treatment set-12, including those patients from the complete set with 12 months or more of continuous Kineret treatment *.
- The long-term treatment set-18, including those patients from the complete set with 18 months or more of continuous Kineret treatment *.
- The long-term treatment set-24, including those patients from the complete set with 24 months or more of continuous Kineret treatment *.
- The MAS-1 set, including patients with SJIA who have been diagnosed a first time with MAS following start of Kineret treatment

*For the long-term treatment set-12, 18 and 24 the longest continuous treatment period will be considered for inclusion in the sub-population. Hence, an index date may be set for patients who stopped Kineret treatment and later restarted and remained on treatment for a longer period than the previous.

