8.7.4 Incidence rates of Adverse events in sub-population

In a sub-population constituting those with more than 12 months of continuous treatment with Kineret, incidence rates of non-serious AEs of at least moderate severity, all serious AEs and MAS will be calculated for the time after 12 months and in addition incidence rates will be retrospectively derived for each preceding time window (i.e. 1-6, 7-12 months). Similarly, the analysis will also be performed for the subgroup of patients that have more than 18 (preceding windows to present: 1-6, 7-12 and 13-18 months) and 24 (preceding windows to present: 1-6, 7-12, 13-18 and 19-24 months) months of continuous treatment with Kineret respectively. These analyses will enable descriptive comparisons of incidence early in the treatment cycle and incidence resulting from long-term treatment. In the interpretation of the incidence rates calculated for the sub-populations, respective incidence rate for the total study population (the complete set) will also be taken into account. Interruptions of treatment, e.g. treatment holidays, will be allowed for up to 30 days with respect to the definition of continuous treatment. Neither AEs nor patient-time will be counted during the interruption.

Only events that occur when patients are on Kineret treatment exposure (including an additional period of 2 days after treatment stop will be counted.

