8.7.5 Duration of treatment and reasons for discontinuation

Summary statistics for the duration of Kineret treatment will be presented overall and by time window.

The reasons for Kineret treatment discontinuation for more than 30 days will be summarized with number and percentage. The reasons for discontinuation will be collected as per the Pharmachild CRF: adverse event (moderate/severe/serious event or mild event), intolerance, dose change, inefficacy, remission, surgery, pregnancy or other reason. A patient can contribute with multiple discontinuations if starting a new treatment period after a treatment holiday of more than 30 days. Furthermore, multiple reasons can be recorded for one single discontinuation

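### Taking each patient's longest course for long-term sets 12, 18 and 24 selects on the outcome, and lowers rates of treatment-ending AEs when AE-stopped patients restart

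*Protocol*

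**What the plan says.** Protocol section 8.7 defines long-term treatment set-12 as "including those patients from the complete set with 12 months or more of continuous Kineret treatment", with parallel definitions at 18 and 24 months. The footnote to the three sets adds that "the longest continuous treatment period will be considered for inclusion in the sub-population" and, as a consequence, that "an index date may be set for patients who stopped Kineret treatment and later restarted" and stayed on longer than before.

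Section 8.7.4 uses these sets to set early incidence beside long-term incidence. For set-12 the rates "will be calculated for the time after 12 months and in addition incidence rates will be retrospectively derived for each preceding time window"; the 18- and 24-month sets follow the same pattern. Gaps "will be allowed for up to 30 days with respect to the definition of continuous treatment".

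Section 8.7.5 lists adverse events among the recorded reasons for stopping and expects repeat courses: "A patient can contribute with multiple discontinuations if starting a new treatment period after a treatment holiday of more than 30 days".

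Section 8.9 concedes that patients who stay on treatment may be those who had few events beforehand, and offers the complete set as a comparison. It does not mention choosing among one patient's own courses.

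**The concern.** How long a course lasted is known only when it ends, and an adverse event is one of the things that ends it. A course cut short by an event is therefore less likely to be a patient's longest. Where a patient has two courses that each pass the threshold, the rule tends to keep the one that was not cut short.

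Suppose a patient has a 14-month course ended by an SAE in month 14, and later a 20-month course without events. Both satisfy the 12-month rule. With the index moved to the second course, an SAE that occurred after 12 months of continuous treatment is absent from set-12.

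Long-term safety is the study's stated objective (section 7), and these sets are its main tool for describing incidence under prolonged treatment. Sections 8.6 and 9.1 say that only summary output will be obtained, so the sponsor could not rebuild the dropped courses from listings afterwards.

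**Working it through.** The protocol attaches no rate, event count or power figure to this rule, so there is no stated figure to reproduce. The share of patients with two qualifying courses, the stopping hazards and the restart probabilities are not given either. All of these are assumptions below.

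**1. The example.** Post-month-12 time is 2 months in the first course and 8 months in the second. Counting both courses gives 1 event in 10 months; the longest course alone gives 0 events in 8 months. Time is dropped along with the event, but the two do not cancel.

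**2. A model that can be checked by hand.** Beyond the threshold, let a course end by AE at hazard L and for other reasons at hazard M, both constant, with no censoring and at most two qualifying courses per patient. Write p = L/(L+M). Let a be the share of AE-ended qualifying courses that are followed by a second qualifying course, and b the same share after other stops. The share of set patients with two is f = pa + (1−p)b. Mean post-threshold time is 1/(L+M) for one course and 1.5/(L+M) for the longer of two. Which course is longer is independent of how each ended.

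Events per patient kept by the longest-course rule:
- one course, ended by AE: p(1−a)
- two courses, first ended by AE: pa(½ + ½p)
- two courses, first ended otherwise: (1−p)b·½p
- sum: p(1 − a/2 + f/2)

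Time per patient: (1 − f + 1.5f)/(L+M) = (1 + f/2)/(L+M).

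Rate = L(1 + f/2 − a/2)/(1 + f/2), so the relative bias is −(a/2)/(1 + f/2).

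The first-course rule gives p divided by 1/(L+M), which is L. Counting all qualifying courses gives p(1+f) divided by (1+f)/(L+M), which is also L. Both are unbiased in this model.

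**3. Size when restart is equally likely after either kind of stop (a = f).** The rate becomes L/(1 + f/2).

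| f (assumed) | Rate too low by |
|---|---|
| 2% | 1.0% |
| 5% | 2.4% |
| 10% | 4.8% |
| 20% | 9.1% |
| 30% | 13.0% |
| 40% | 16.7% |

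**4. When it vanishes.** If AE-stopped patients never restart, a = 0 and the bias is exactly zero. AEs that do not end treatment carry no information about course length, so their rate is unaffected; in simulation it was about 10.0 per 100 patient-years under either rule.

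**5. The narrower reading.** If only an earlier shorter course is dropped and a later shorter one is kept, events are p(1 + f − a/2) and time is (1 + 0.75f)/(L+M). At a = f = 20% the ratio is 1.1/1.15, or 4.3% low. At a = 0 and f = 20% it is 1.2/1.15, or 4.3% high.

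**6. Simulation with censoring.** Assumed: AE-stop hazard 0.05-0.15 per year, other stops 0.2-0.5 per year, restart probability 0-0.5 after an AE and 0.3-0.8 otherwise, follow-up 1-12 years, up to four courses. Compared with counting all qualifying courses, longest-course rates of treatment-ending AEs, when some AE-stopped patients restart, were:
- set-12: 3-14% low (f 11-38%); for example 4.52 against 5.00 per 100 patient-years at f = 23%
- set-18: 2-10% low
- set-24: 2-7% low

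Without restarts after AEs the difference was 0% to +1%. Under the narrower reading, set-12 was 1-6% low with such restarts and about 5% high without. A separate simulation with other assumed inputs put set-12 about 8-18% low, and the first-course and all-courses rules both recovered the true rate.

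**7. Does the complete-set comparison repair it?** Complete-set windows run in calendar time from baseline (8.7.1), which is the first injection (8.7.2.2). In the example, with an assumed 3-month gap, month 13 of the second course is month 14 + 3 + 13 = 30 from baseline. That is month 13-18 on the re-indexed clock but beyond 24 months in the complete set. For such patients the windows do not line up.

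**The case against.** The strongest reply has four parts.

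- **The footnote may only govern membership.** Having a longest course of at least 12 months is the same as having any course of at least 12 months, so nobody is lost. A reader might infer that every shorter qualifying course is discarded, but the protocol does not say so: the new index date is permissive, and a shorter course after the longest one is not addressed. This limits the claim. It does not remove it, because moving the index to a later course leaves the earlier one outside the 8.7.4 windows on the natural reading.
- **The bias is not general.** A reader might infer that all long-term rates come out low. Steps 4 and 5 show otherwise: the bias needs two qualifying courses in one patient, AEs that end treatment, and restart after such AEs. This stands in full.
- **Sampling error is larger.** With 15 to 50 post-month-12 events (assumed), the approximate Poisson 95% half-width is 1.96/√15 = 51% to 1.96/√50 = 28%. That is true, and it bears on severity. But an avoidable error whose direction depends on who restarts is not described by the confidence interval.
- **The events are not lost to the study.** The complete set counts all on-treatment events, and sections 8.7.4 and 8.9 commit to reading the sub-populations against it. This also stands, although the windows are misaligned for re-indexed patients.

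One might also object that the early windows of a re-indexed course describe re-exposure. That does not favour either rule: after a 5-month course followed by a 20-month one, the first qualifying course is also a restart.

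**Conclusion.** The point holds in a limited form. The footnote fixes a selection by realised course length, and that selection depends on the outcome because AEs can end courses. Post-threshold rates of treatment-ending AEs are then too low by about 1-5% if 2-10% of set patients have two qualifying courses, and by about 8-18% if 20-40% do. These shares are assumed; the figures also rest on roughly constant hazards, on restarts after AE-related stops, and on only the longest course being counted. If later shorter courses are kept, the effect is smaller and can reverse.

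The documents do not support saying that long-term rates are understated in general, or that the SAE in the example disappears from the study. The analyses are descriptive and the complete set keeps the events. The issue is moderate: worth correcting before extraction, but not a reason to hold the study.

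**What to change.** In sections 8.7 and 8.7.4, replace the longest-course rule by one of two options:

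- **First qualifying course:** the first continuous course to reach 12 (18, 24) months, applied separately at each threshold and indexed at the start of that course.
- **All qualifying courses:** every course that reaches the threshold, each indexed at its own start, with the cluster-robust variance that 8.7.1 already specifies.

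State explicitly whether courses before and after the chosen one contribute. Keep the longest-course analysis as a sensitivity analysis, report for each set how many patients had more than one qualifying course, and add to 8.9 a sentence naming selection among a patient's own courses.

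The cost is a few sentences, and Annex 1 says the SAP is still to be finalised before data collection. The first-course option gives up some person-time relative to the longest course: in the model above, 1/(1 + f/2), or 4.8% less post-threshold time at f = 10%. The all-courses option loses no qualifying time but needs slightly more programming.

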8.7.1 Incidence rates of Adverse events

The analyses will include calculation of unique incidence rates (with 95% CI) of each reported non-serious AE (moderate and severe), SAE and MAS as an ESI respectively. A patient may contribute with multiple events of the same AE term. Incidence rate of events (calculated as the number of the incident events divided by the sum of patient years under risk) will be expressed

as incidence rate per 100 patient years. The incidence rate will be derived by a Poisson regression model (with only intercept) and the 95% CI will be estimated using the Poisson estimator with a cluster-robust estimate of variance to control for both overdispersion and intracluster correlation. AE specific incidence rates will be presented overall for the complete study period and by time windows defined with reference to baseline. The time windows will be defined as follows: 1-6 months, 7-12 months, 13-18 months, 19-24 months and >24 months of calendar time. AEs and patient-time will only be counted during Kineret treatment exposure that includes an additional period of 2 days (i.e. slightly longer than 5 half-lives in patients without renal impairment after treatment stop).

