8.7.2 Additional analyses of the incidence of MAS

8.7.2.1 Analysis of first occurrence and recurrence of MAS

The incidence rate of MAS will also be analyzed with respect to 1st occurrence and recurrence respectively. The rationale for this is to account for a biological distinction in altered risk following a first event. For the analyses, the 1st occurrence of MAS is defined to occur at or after baseline regardless of whether the patient had a history of MAS or not. The patients included in the risk set for a 2nd occurrence of MAS are only those who had a 1st occurrence of MAS as defined above. Likewise, the patients included in the risk set for a 3rd occurrence of MAS are only those who had a 2nd occurrence of MAS etc. MAS events and patient-time will only be counted during Kineret treatment exposure that includes an additional period of 2 days after treatment stop.

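### The only interval method for incidence rates gives no 95% CI at zero events and can be falsely narrow in very small risk sets, such as recurrent MAS

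*Protocol*

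**What the plan says.** Section 8.7.1 of the protocol defines the incidence rate as events over exposure, "calculated as the number of the incident events divided by the sum of patient years under risk", and derives it from a Poisson regression containing only an intercept. For the interval, "the 95% CI will be estimated using the Poisson estimator with a cluster-robust estimate of variance", the stated purpose being "to control for both overdispersion and intracluster correlation". The cluster is not named. I take it to be the patient, because the same section states: "A patient may contribute with multiple events of the same AE term".

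The scope is wide. The section asks for "calculation of unique incidence rates (with 95% CI) of each reported non-serious AE (moderate and severe), SAE and MAS as an ESI respectively", overall and in five windows: "1-6 months, 7-12 months, 13-18 months, 19-24 months and >24 months of calendar time". Section 8.7.2.1 adds MAS rates by order of occurrence, with risk sets that shrink at each step: "the patients included in the risk set for a 3rd occurrence of MAS are only those who had a 2nd occurrence". Section 8.7.4 adds rates by window in patients treated continuously for more than 12, 18 and 24 months. Neither section names a different interval.

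The only small-number rule in the protocol is in section 8.7.2.3, where the stratified Kaplan-Meier curve is dropped if a subgroup has 10 patients or fewer. Section 8.5 expects about 300 patients without a formal calculation.

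**The concern.** A log-link Poisson model with a sandwich variance needs events in order to work. With none, the log-rate has no finite estimate and the standard error is 0/0. With very few patients, the sandwich is built from a handful of residuals that can all be close to zero, so the interval can collapse around the estimate.

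Both situations are foreseeable here. The study was agreed with EMA to look further at long-term safety and the potential risk of MAS (section 6). When a window shows no MAS, the upper limit is the informative result, and the plan as written supplies none. When two or three patients have recurrent MAS, a very narrow interval would suggest knowledge that the data do not contain.

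**Working it through.** **Inputs.** Patients: Table 1 in section 8.4 gives 212 + 95 = 307 SJIA patients treated with Kineret, which agrees with the approximately 300 in section 8.5. The protocol gives no event rates, MAS counts or patient-years, so the PY values below are assumptions unless derived from 307 patients.

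**Formulas.** With D events over T patient-years in G patients, rate = D/T. The robust SE of the log-rate is √[G/(G−1) × Σ(yᵢ − rate × tᵢ)²] / D, and the CI is rate × exp(±1.96 × SE). The comparator is the exact Poisson (Garwood) interval.

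**1. Zero events.** The ratio gives 0. The model has no finite log-rate and the SE is 0/0, so there is no interval. The exact upper limit is 3.69/T: 9.2 per 100 PY at an assumed 40 PY, and 2.4 at 154 PY.

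**2. Low counts in a large set** (300 patients, 0.5 years each, 150 PY assumed; per 100 PY):

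| Events | Robust 95% CI | Exact 95% CI |
|---|---|---|
| 1 | 0.09 to 4.73 | 0.02 to 3.71 |
| 2, in two patients | 0.33 to 5.32 | 0.16 to 4.82 |
| 2, in one patient | 0.19 to 9.47 | 0.16 to 4.82 |
| 5, in five patients | 1.40 to 7.96 | 1.08 to 7.78 |

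The robust lower limit is too high at one or two events. By five events the methods nearly agree. When both events come from one patient, the robust upper limit is about twice the exact one, because only the robust method sees the clustering.

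**3. Coverage** (simulation, 6,000 runs per setting, 300 patients, no overdispersion). Given at least one event, the robust interval covers in 97%, 94%, 97%, 97% and 96% of runs at 1, 2, 3, 5 and 10 expected events, and in 77% at 0.5. With 20, 10 or 5 patients and one expected event, the figure is 88%, 90% and 93%. Exact coverage is 96 to 99% at expected counts from 0.5 to 20. Under strong overdispersion (assumed gamma frailty variance 20) exact coverage drops to 92% at 10 expected events and 82% at 20, while the robust interval holds 95% and 93%.

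**4. Very small risk sets.**
- Three patients, one event each, over 1.0, 1.5 and 0.8 years: rate = 3/3.3 = 90.9 per 100 PY. Residuals are 0.091, −0.364 and 0.273, and their squares sum to 0.215. SE = √(1.5 × 0.215)/3 = 0.189, giving 63 to 132. The exact interval is 19 to 266.
- Two or three patients with one event each over equal time: every residual is zero and the interval has zero width.
- Two patients, one event, in the patient with 90% of the time: Σ residual² = 1 − 1.8 + 0.82 = 0.02, or 0.04 after the factor G/(G−1) = 2. SE = 0.2, so the limits are exp(±0.392) = 0.68 to 1.48 times the rate. The exact limits are 0.025 to 5.57 times.

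**5. Where sparse cells can arise.** A six-month window holds at most 307 × 0.5 = 153.5 PY. Expecting five events there needs 5/153.5 = 3.3 per 100 PY. Zero events is at least as likely as not when the rate is ln 2/153.5 = 0.45 per 100 PY or lower. For an assumed rate of 1 to 5 per 100 PY, the chance of zero events is 67% to 14% at 40 PY, and 21% to under 0.1% at 154 PY.

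**The case against.** The best counter-argument is that low-count handling belongs in the SAP. Annex 1 lists one, to be finalised before data collection, and it is not at hand. The robust variance is a sound main choice, and naming it does not forbid a supplementary rule. The study is also descriptive, so no test or threshold depends on a confidence limit. The SAP may indeed contain such a rule. But the protocol does more than stay silent: it prescribes one method for each reported term and each window, and an SAP that follows it literally inherits the failure.

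Several stronger readings are tempting, and the documents do not support them:

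- *No rate at zero events.* The ratio in section 8.7.1 gives 0 per 100 PY. Only the interval is missing.
- *Most cells are sparse.* No event rates or patient-years are given. Only reported terms are tabulated, so a term has at least one event somewhere, and the overall and >24-month cells are not limited to 154 PY.
- *The interval covers only about 61%, 82% and 92% of the time at 1, 2 and 3 expected events.* Those simulated figures count every zero-event run as a miss. Given an event, coverage with 300 patients is 94 to 97% in that range.
- *One event always gives 0.14 to 7.1 times the rate.* This holds in large sets with similar exposure. The two-patient example above gives 0.68 to 1.48.

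A further objection stands and shapes the remedy. A blanket switch to exact limits below five events would cut the upper limit for two events in one patient over 150 PY from 9.5 to 4.8 per 100 PY, discarding the clustering that the robust variance is there to capture.

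**Conclusion.** The point holds as a gap in a stated rule. The prescribed method gives no interval at zero events and can give a falsely narrow or zero-width one in very small risk sets, chiefly second and later MAS occurrences. In large sets with at least one event it is broadly adequate, with limits shifted upward at one or two events, and from about five events there is no case for replacing it. Robust variance should therefore remain the main method. How many cells are affected cannot be determined from the protocol. The bound of about 154 PY makes zero and low counts likely for individual terms in six-month windows, and the narrowing MAS risk sets make them likely for recurrences. The 40 PY and 150 PY illustrations, the three-patient exposure times and the frailty variance are assumptions.

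**What to change.** Add a low-count rule to section 8.7.1, or to the SAP with a cross-reference:

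- **Zero events with patient-time at risk:** report a rate of 0 with the exact Poisson upper limit, 3.69 divided by the patient-years.
- **1 to 4 events, no patient contributing more than one:** use the exact Poisson (Garwood) interval. Rates by MAS order meet this condition by construction, since a patient can have only one event of a given order.
- **One patient contributing several of the events, or 5 or more events outside the MAS-order rates:** keep the robust interval and state that the cluster is the patient.
- **MAS-order rates in a very small risk set:** use the exact interval at any count. The SAP should define very small; the limit of 10 patients already used in section 8.7.2.3 is a possible choice. With 5 or more events in a larger risk set, the robust interval can stay.
- **Empty risk set:** report as not estimable, since with no patient-time the exact limit does not exist either.

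Show the number of events and of patients with an event in each cell, so that a reader can see which interval applies. The rule must be settled before output is produced: under sections 8.6 and 9.1 the sponsor receives summaries only and could not recompute robust intervals afterwards. The cost is a few sentences, a second interval method to footnote in the tables, and slightly conservative limits at low counts.
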